9.3. Data Analysis Considerations

9.3.1. Analysis Populations

The primary population for all analyses of MACE and other time to event outcomes will be the All Randomized (ITT) Population. Subjects will be analyzed according to the treatment to which they were randomized.

The primary population for the Hgb efficacy analyses will also be the ITT Population. A supportive analysis of the primary efficacy endpoint will be performed in a Per-Protocol (PP) Population defined as all ITT subjects who are not major protocol violators. Details will be defined in the RAP and subjects analyzed according to the treatment received.

The primary population for safety will be based on all randomized subjects who receive at least one dose of randomized treatment. Subjects will be analyzed according to the treatment received.

Additional populations may be defined in the RAP, including sub-study populations.

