12.13.2. Objectives and Endpoints

Objectives	Endpoints
Primary	

 To compare daprodustat to darbepoetin alfa for effect on SBP (superiority) by ABPM in ND subjects in the ABPM ITT population 	
 Change in 24 hour average SBP from baseline to end of sub-study¹ between treatment groups
Secondary	

 To assess the effect of daprodustat and darbepoetin alfa independently 	
 Change in 24 hour average SBP from baseline to end of sub-study¹ within each treatment group

Objectives	Endpoints
on SBP, DBP and mean arterial blood pressure (MAP) by ABPM in the ABPM ITT population	
 • Change in 24 hour average DBP from baseline to end of sub-study¹ within each treatment group • Change in 24 hour average MAP from baseline to end of sub-study¹ within each treatment group

 • To compare the effect of daprodustat to darbepoetin alfa on DBP and MAP by ABPM in the ABPM ITT population 	
 • Change in 24 hour average DBP from baseline to end of sub-study¹ between treatment groups • Change in 24 hour average MAP from baseline to end of sub-study¹ between treatment groups

 • To compare the effect of daprodustat to darbepoetin alfa on BP parameters in the ABPM per-protocol population 	
 • Change in 
 ○ 24 hour average SBP ○ 24 hour average DBP ○ 24 hour average mean arterial pressure from baseline to end of sub-study¹ between treatment groups

 • To compare daprodustat to darbepoetin alfa on BP parameters in the ABPM per-protocol population 	
 • Change in: 
 ○ 24 hour average SBP ○ 24 hour average DBP ○ 24 hour average mean arterial pressure from Baseline to end of sub-study¹ within each treatment group

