12.13.3.5. Antihypertensive Medication Changes

It is preferred that no changes are made to antihypertensive medications while the subject is part of the sub-study.

If changes in antihypertensive medications are necessary, these must be documented in the eCRF along with the reasons. Subjects will remain in the sub-study regardless of any change.

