12.13.4. Sample Size and Power Calculations

The sample size of this sub-study has been designed based on the primary sub-study objective to demonstrate superiority in average SBP change from baseline to end of sub-study between arms (daprodustat versus darbepoetin alfa), measured by ABPM over a 24 hour assessment period. Assuming a one-sided 2.5% significance level, a true standard deviation for SBP change from baseline measured by ABPM of 11 mmHg [Peixoto, 2000], and up to a 20% withdrawal rate from the sub-study, a sample size of 68 subjects per group (136 subjects in total) will provide greater than 80% power to detect a -6 mmHg difference in treatment groups (i.e., achieve superiority). Given the planned sample size, superiority will be established if there is more than a 4.2 mmHg mean difference observed in favor of daprodustat.

Assuming a 40% screen failure rate for the additional ABPM entry criteria, approximately 228 subjects that are eligible for the main study will need to be screened for the sub-study in order to randomize approximately 136 subjects. See Section 9.2.3 for more information about sample size adjustments.

Unblinded ABPM data will be reviewed by the IDMC during the conduct of the trial as part of their data monitoring responsibilities. No interim analysis is planned.

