12.13.5. Statistical Analysis

The primary sub-study estimand is to compare the treatment effect on change from baseline in 24 hour average SBP at end of sub-study, in all randomized sub-study subjects. The statistical model for analysis will be an ANCOVA with terms for treatment and baseline 24 hour average SBP. This model will provide a point estimate and two-sided 95% CI for the treatment effect and a one-sided p-value for the superiority

assessment. Superiority will be established if the p-value is <0.025 . The primary analysis population will be the ABPM sub-study-ITT population defined as randomized subjects who were also entered into the ABPM sub-study.

Given the nature of ABPM measurement, a high degree of dropout unrelated to randomized treatment is anticipated. The potential high level of missing data poses a challenge in the interpretation of the primary ABPM sub-study analysis. The reason for missing ABPM data will be examined to explore the impact of missing data on the sub-study primary efficacy conclusions. If the majority (defined as $\geq 70\%$) of the missing data is due to either subject unwillingness to repeat the ABPM procedure or due to an unevaluable reading, then data will be treated as missing at random and the primary analysis will be considered sufficient. Otherwise, a sensitivity analysis may be performed that will use multiple imputation from the active control arm to replace data from both treatment groups that was missing due to reasons other than subject unwillingness or unevaluable readings. Further supplementary analyses may include an ABPM per-protocol population (PP) analysis, utilizing all ABPM-ITT subjects who are not major protocol violators or who did not change BP medications during the sub-study. Further details of sensitivity and supplementary analyses will be described in the RAP.

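### As printed, the ABPM per-protocol rule removes only subjects who are both major protocol violators and BP-medication changers

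*Protocol*

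**What the plan says.** The ABPM sub-study's primary population is ABPM-ITT. Section 12.13.5 then adds: "Further supplementary analyses may include an ABPM per-protocol population (PP) analysis", which it describes as "utilizing all ABPM-ITT subjects who are not major protocol violators or who did not change BP medications during the sub-study". It closes with "Further details of sensitivity and supplementary analyses will be described in the RAP".

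Section 12.13.2 uses the per-protocol population in five secondary objectives. Two are for that population alone: "To compare the effect of daprodustat to darbepoetin alfa on BP parameters in the ABPM per-protocol population" (between-group change), and a companion objective on within-group change. The other three name both the ITT and the per-protocol populations: the dipping pattern, conversion from non-dipper to dipper, and conversion from dipper to non-dipper.

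Two other places bear on what the rule should do:

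- Section 9.3.1 gives the main-study per-protocol set as "defined as all ITT subjects who are not major protocol violators".
- Section 12.13.3.5 says of antihypertensives: "It is preferred that no changes are made to antihypertensive medications while the subject is part of the sub-study". If a change is needed it is documented, and "Subjects will remain in the sub-study regardless of any change".

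**The concern.** A per-protocol set is meant to take out subjects whose data depart from the protocol. The printed rule lists two conditions for staying in, no major violation and no BP-medication change, and joins them with *or*. Meeting one is then enough, so each condition lets back in the subjects the other was meant to exclude.

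For violators, the rule is weaker than the sponsor's own concept in Section 9.3.1. For changers, Section 12.13.3.5 discourages a change but does not call it a violation, so the second condition is where they would be excluded. With *or*, that condition removes no changer who is not also a major violator.

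At stake is whether the per-protocol versions of the five secondary objectives describe the population their name implies. An RAP that follows the protocol inherits the slip, and one that uses *and* contradicts it. Membership should be settled before unblinding, because a choice between the two readings made afterwards would be open to challenge.

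**Working it through.** **The plan's own figure.** The per-protocol definition carries no number. The related figure is the sub-study size in Section 12.13.4: "a sample size of 68 subjects per group (136 subjects in total) will provide greater than 80% power to detect a -6 mmHg difference". Inputs given there: one-sided 2.5% level, SD 11 mmHg, up to 20% withdrawal.

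- Per arm for 80% power: n = 2 × (1.960 + 0.842)² × 11² / 6² = 52.8, so 53. Allowing for withdrawal: 53 / 0.80 = 66.3, so 67, against 68 stated.
- Evaluable per arm: 68 × 0.80 = 54. Power is 0.80 (t) to 0.81 (normal).
- Observed difference needed: t(0.975, 106) × 11 × √(2/54) = 4.20 mmHg, against 4.2 stated.

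The size reproduces, so 136 is used as the denominator below.

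**The logic.** Let V = major violator and C = BP-medication changer. The printed rule keeps (not V) or (not C), which equals not (V and C). The rule with *and* keeps (not V) and (not C), which equals not (V or C).

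| Subject | Printed rule (*or*) | Rule with *and* |
|---|---|---|
| no violation, no change | kept | kept |
| no violation, change | kept | dropped |
| violation, no change | kept | dropped |
| violation and change | dropped | dropped |

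This result needs no assumption. The two rules differ in the two middle rows.

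**Size, as an illustration.** Let v and c be the proportions of violators and changers.

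- Changers: Appendix 4 (worsening of hypertension) gives antihypertensive increases in non-dialysis subjects of 25/170 (15%) on daprodustat and 18/80 on control over 24 weeks, and 38% and 45% over 52 weeks. The control figure is printed as 14%, but 18/80 is 22.5%, which is used here. Range taken: 15% to 45%.
- Violators: no rate is given. Assumed: 5% to 20%.
- Overlap: not given. Two cases are shown.

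If V and C are independent, the printed rule drops v × c and the *and* rule drops 1 − (1 − v)(1 − c). If they overlap as much as possible, the printed rule drops min(v, c) and the *and* rule drops max(v, c). In both cases, the share of subjects the *and* rule would remove but the printed rule keeps is 1 − (first / second).

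| v | c | Independent: *or* / *and* drop, of 136 | Share kept | Maximal overlap: *or* / *and* drop, of 136 | Share kept |
|---|---|---|---|---|---|
| 5% | 15% | 1.0 / 26.2 | 96% | 6.8 / 20.4 | 67% |
| 5% | 45% | 3.1 / 64.9 | 95% | 6.8 / 61.2 | 89% |
| 10% | 30% | 4.1 / 50.3 | 92% | 13.6 / 40.8 | 67% |
| 20% | 22.5% | 6.1 / 51.7 | 88% | 27.2 / 30.6 | 11% |
| 20% | 45% | 12.2 / 76.2 | 84% | 27.2 / 61.2 | 56% |

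Over the combinations tried, the share kept runs from 84% to 96% under independence and from 11% to 89% under maximal overlap. With 20% withdrawal (136 × 0.80 = 109 subjects) the counts shrink by a fifth and the shares do not change.

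**The case against.** The strongest reply is that this is loose English in an optional analysis. The per-protocol analysis is one that may be done, details go to the RAP, and the intent is easy to guess from Section 9.3.1. The primary ABPM population is ITT. All five objectives have an ITT counterpart. The 4 mmHg within-group criterion in Section 12.13.5 is estimated from the primary model. Recruitment to the sub-study is already closed. All of this stands, and it limits the weight of the point. It does not remove it: the protocol does not leave membership open but prints a rule, and that rule gives the wrong set. No other place in the protocol restates it with *and*.

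A reader might infer that nearly everyone the rule was meant to remove stays in. The documents do not support that. It depends on an assumed violator rate and on independence. The change rates come from 24- and 52-week studies, whereas the sub-study ends at Week 16, or Week 28 for early completers. Section 12.13.3.2 also requires a stable antihypertensive regimen before entry and an average awake SBP of at most 150 mmHg. Against this, the Appendix 4 figures count increases only, while the rule concerns any change.

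A reader might also infer that the corrected set would show a BP effect free of medication changes. It would not. A medication change follows randomization and is itself an endpoint in Section 12.13.2. Excluding subjects whose treatment was intensified can remove those whose pressure rose, which may itself hide a pressor effect.

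**Conclusion.** The point holds as a wording error that changes who is in the set. Taken literally, Section 12.13.5 removes only subjects who are both major violators and BP-medication changers. That conclusion rests on logic alone. That both groups were meant to be excluded is an inference from the purpose of a per-protocol set and from Section 9.3.1, and it is a strong one.

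The size cannot be determined from the protocol. The ranges above show that the two rules can give very different sets, but they are illustrations under assumed rates and overlap. The consequence is confined to the per-protocol versions of five secondary sub-study objectives. The primary ABPM comparison and the main-study conclusions do not depend on it. Whether the RAP already uses the right rule could not be checked.

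**What to change.** In Section 12.13.5, replace the *or* between the two conditions with *and*, so that a subject must have no major violation and no BP-medication change during the sub-study. State that a change means a change in number or dose, matching the medication endpoints in Section 12.13.2. Use the same definition in the RAP, fixed before unblinding.

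The edit is one word and a short clarification. The price is a smaller per-protocol set with wider confidence intervals, and exclusion on a post-randomization event. The RAP should therefore say that the per-protocol result only supports the ABPM-ITT result and is not an estimate of a medication-free BP effect.

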12.13.1. Introduction and Rationale

Hypertension is one of the major risk factors associated with cardiovascular morbidity and mortality and is common in patients with advanced CKD Stages 3b through 5.

Treatment of anemia associated with CKD using ESAs has the associated risk of increased BP, especially during the period of hemoglobin correction. ESA-induced elevation of BP often necessitates initiation of, or increases in, antihypertensive medications in patients with CKD. While SBP and DBP are both of prognostic importance, SBP is the overall best predictor of future cardiovascular risk in a hypertensive population [Peters, 2013]. Therefore, SBP was chosen as the primary endpoint in this ABPM sub-study. ABPM is being used to measure BP in this sub-study because previous studies have used this BP measurement modality in subjects with CKD to establish an association with mortality [Agarwal, 2010].

This sub-study is intended to compare daprodustat to darbepoetin alfa on BP as assessed by ABPM in ND subjects with anemia associated with CKD.

While multiple mechanisms likely underlie ESA-induced hypertension, reduced urinary sodium excretion is hypothesized to be a major mechanism by which ESAs potentiate hypertension and non-responsive BP dipping in patients with CKD [Krapf, 2009]. Patients with CKD may also excrete less urinary sodium since they have lower levels of renal nitric oxide (NO). Patients with CKD produce more reactive oxygen species that reduces NO, and NO normally stimulates urinary sodium excretion [Ge, 2006]. As daprodustat activates HIF signaling, and one of the downstream targets of HIF is nitric oxide synthase, daprodustat may augment urinary sodium excretion, reduce SBP and restore a responsive nocturnal BP dipping pattern. Therefore, in addition to comparing the effects of daprodustat to darbepoetin alfa on SBP in this sub-study, an exploratory objective is to compare urinary sodium and aldosterone excretion with daprodustat versus darbepoetin alfa, which may include excretion over 24 hrs or normalized to urinary creatinine.

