
 • To compare the percentage of subjects in each treatment group requiring a change in antihypertensive medications in the ABPM ITT population 	
 • Difference between treatment groups in percentage of subjects requiring no change in number or dosage of antihypertensive medications • Difference between treatment groups in percentage of subjects requiring an increase in number or dosage of antihypertensive medications • Difference between treatment groups in percentage of subjects requiring a decrease in number or dosage of antihypertensive medications

 • To characterize the dipping pattern of sleeping BP in each treatment group in the ABPM ITT and ABPM per-protocol populations 	
 • 24-hour BP profile as measured by ABPM, with subjects categorized according to their sleeping BP behaviors as: • dippers (normal) when the reduction in the average SBP during the sleeping period was >10% to 20% of mean SBP during waking hours, • extreme dippers when this reduction was >20%, • non-dippers when the reduction was <10%, and • reverse dippers when the mean sleep SBP was higher than the awake SBP [Bakris, 2014]

 • To compare the percentage of subjects that convert from non-dipper status to dipper status between treatment groups in the ABPM ITT and ABPM per-protocol populations 	
 • Difference between treatment groups in percentage of subjects that convert from non-dipper status at baseline to dipper status at end of sub-study¹

 • To compare the percentage of subjects that convert from dipper status to non-dipper status between treatment groups ABPM ITT and ABPM per-protocol populations 	
 • Difference between treatment groups in percentage of subjects that convert from dipper status at baseline to non-dipper status at end of sub-study¹

Objectives	Endpoints

 To compare the effect of treatment with daprodustat to darbepoetin alfa on heart rate by ABPM in the ABPM ITT population 	
 Change from baseline to end of sub-study¹ in 24 hour average heart rate between treatment groups as measured by ABPM relative to time since administration of medication
Exploratory	

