In order to contextualise the primary between-group comparison, a key secondary objective is to assess within-group changes from baseline over the sub-study. Assessment of within-group changes will support interpretation of the primary analysis by identifying whether there was an absence of an increase in BP in one or both treatment groups. To that end, two-sided 95% confidence intervals will be calculated for change from baseline in each ABPM parameter separately for each treatment group. For either treatment group, a lack of adverse effect on the primary endpoint of average SBP at end of sub-study will be concluded if the upper 95% confidence limit is no more than 4 mmHg. This margin was chosen as it is less than the clinically meaningful change of 5 mmHg [Whelton, 2002] and it is half the historical increase in SBP observed with rhEPO [Krapf, 2009].

The mean and two-sided 95% CI will be estimated from the primary statistical model for within treatment arm SBP change from baseline to end of sub-study.

The change from baseline 24 hour average DBP, mean arterial pressure and heart rate at end of sub-study will be assessed in a similar way, as the primary using analogous ANCOVA models with treatment and baseline as covariates.

The differences in proportion of subjects that increase/decrease their BP medication (number or dose) will be assessed using Fisher's Exact Test. The differences between treatment groups in the proportion of subjects that convert from dippers/ non-dippers at baseline to non-dippers/ dippers at end of sub-study will also be assessed using Fisher's Exact Test.

Plots of the mean 24 hour average values (two-sided 95% CIs) and mean changes from baseline in 24 hour average values (two-sided 95% CIs) for BP will be provided by treatment group.

Changes from baseline in 24 hour urine sodium excretion and 24-hour urine aldosterone excretion at end of sub-study will be analyzed in a similar manner to the primary ABPM endpoint, except that the statistical model for analysis will be an ANCOVA with terms for treatment and baseline 24 hour urine parameter.

Additional statistical considerations will be addressed in the RAP.

References

Agarwal RJ. Blood Pressure and Mortality Among Hemodialysis Patients. *Hypertension*. 2010; 55:762-768.

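### ABPM sub-study: nocturnal dipping is tested between arms only as dipper/non-dipper conversion, although a baseline-adjusted analysis of the percent fall would use the same recordings with much more power

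*Protocol*

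**What the plan says.** All references are to Appendix 13 of the Protocol.

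- **Data.** Section 12.13.3.1 has the device record blood pressure every half hour, awake and asleep, over two 24-hour sessions, and has sleep and wake times noted.
- **Classes.** Section 12.13.2 calls a subject a dipper if the fall in mean SBP during sleep is above 10% and up to 20% of the awake mean, and an extreme dipper above 20%. The other two classes read "non-dippers when the reduction was <10%, and" and "reverse dippers when the mean sleep SBP was higher than the awake SBP".
- **Endpoints.** Besides a description of the pattern by arm, Section 12.13.2 lists two between-arm dipping endpoints: the percentage converting from non-dipper to dipper, and the percentage converting the other way.
- **Test.** Section 12.13.5 has the proportions that "convert from dippers/ non-dippers at baseline to non-dippers/ dippers at end of sub-study will also be assessed using" Fisher's exact test.
- **Other measures.** The same section gives 24-hour DBP, MAP and heart rate, and urinary sodium and aldosterone, an ANCOVA with treatment and baseline, as for the primary SBP endpoint.
- **Rationale.** Section 12.13.1 says "daprodustat may augment urinary sodium excretion, reduce SBP and restore a responsive nocturnal BP dipping pattern".

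**The concern.** Dipping status is a cut through a continuous quantity, the percent nocturnal fall, which can be calculated for each subject at both sessions. The plan cuts it at 10% twice, at baseline and at follow-up, and then divides the subjects by starting class into two separate comparisons. How far a subject moves is discarded; only crossing the line counts. Each test also uses only part of a sample that is already small.

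At stake is whether a moderate effect on nocturnal pressure, which the rationale raises as a possibility, would be seen. Recruitment to the sub-study is closed, so a more efficient analysis is the only remaining way to gain precision.

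**Working it through.** **1. Inputs from Section 12.13.4.**
- Level and SD: "Assuming a one-sided 2.5% significance level, a true standard deviation for SBP change from baseline measured by ABPM of 11 mmHg".
- Size: 68 per arm, which allows for as many as 20% withdrawing.
- Claimed power: "will provide greater than 80% power to detect a -6 mmHg difference in treatment groups".
- Smallest observed difference that counts as superiority: just over 4.2 mmHg.
- Evaluable per arm: 68 x 0.8 = 54.4, so about 54.

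**2. The plan's own figures, for 24-hour SBP.**
- n per arm = 2 x 11² x (1.96 + 0.84)² / 6² = 52.7, so 53. With 20% withdrawal, 53 / 0.8 = 66.3, so 67 (stated 68).
- Standard error at 54 per arm = 11 x sqrt(2/54) = 2.117. Power = Φ(6/2.117 - 1.96) = Φ(0.874) = 81%.
- Threshold = 1.983 x 2.117 = 4.20 mmHg.

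These agree with the protocol. It gives no power figure for dipping.

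**3. Assumptions for dipping (none is in the protocol).** Percent fall is bivariate normal at the two sessions, with SD 7 percentage points; only the effect/SD ratio matters. Baseline non-dippers are 50-80% and the within-subject correlation r is 0.3-0.7. Treatment shifts the follow-up mean. A fall of 10% or more counts as dipper (extreme dippers included) and anything below 10% as non-dipper (reverse dippers included). The denominator is the subjects in the starting class.

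**4. Effect size.** For 80% ANCOVA power the shift is (1.96 + 0.84) x 7 x sqrt(1 - r²) x sqrt(2/54). At r = 0.5: 2.80 x 7 x 0.866 x 0.1925 = 3.27 points, raised by 1% for the t distribution to 3.30.

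**5. Central case (65% baseline non-dippers, r = 0.5, shift 3.30; 4,000 simulated trials).** Conversion from non-dipper to dipper is 41.8% against 23.6%, among about 0.65 x 54 = 35 subjects per arm.

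| Test, one-sided 2.5% | Power |
|---|---|
| ANCOVA of percent fall | 81% |
| Fisher, non-dipper to dipper | 29% |
| Fisher, dipper to non-dipper | 15% |
| Either Fisher test, no multiplicity control | 40% |

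As a check, the uncorrected normal approximation for 41.8% against 23.6% with 35 per arm gives 36%. Fisher's test is conservative, so 29% is in line. Fisher's power for non-dipper to dipper is 73% at 150 evaluable per arm and 86% at 200, so 80% needs roughly 175 or more, against 54.

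**6. Whole grid (2,500 trials per scenario).**

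| ANCOVA power | Non-dipper to dipper | Dipper to non-dipper | Either | Share of power lost, non-dipper to dipper |
|---|---|---|---|---|
| 80% | 19-36% | 7-22% | 25-44% | 56-76% |
| 90% | 25-47% | 8-29% | 33-56% | 49-72% |
| 95% | 31-57% | 9-35% | 39-66% | 40-67% |
| 99% | 43-73% | 13-48% | 56-81% | 26-56% |

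Repeat simulations at the 80% benchmark gave 17-34%, 6-22% and about 25-42% for the three Fisher columns. Over all runs the ranges are therefore about 17-36%, 6-22% and 25-44%. With all subjects as the denominator, non-dipper to dipper falls to 13-31%.

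**The case against.** The strongest reply is that Fisher's test fits the endpoint as written. Section 12.13.2 asks for a difference in conversion percentages, Fisher's test is valid for that, and a mean shift in percent fall is a different question. This stands as far as validity goes. It does not remove the power loss, and the plan offers no other between-arm test of dipping.

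Little also rests on the endpoint. The sub-study is sized on 24-hour SBP only, and dipping carries no power claim, alpha allocation or decision rule. That stands and limits the weight of the point. The analysis plan, which is not shown and to which Section 12.13.5 leaves additional considerations, may add a continuous analysis. The comment concerns only what the protocol fixes.

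A reader might infer more than the documents support:

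- *That more than half of the power is always lost.* This depends on the 80% benchmark and the assumed inputs. At 99% ANCOVA power the loss for non-dipper to dipper is 26-56%, and counting either test as a success gives a 45-69% loss at 80%.
- *That only subjects close to 10% are used.* Every baseline non-dipper enters one comparison and every baseline dipper the other.
- *That the cut has no regulatory or guideline standing.* The protocol shows only that a study is cited; nothing more can be checked from it.
- *That restored dipping is a formal hypothesis.* Section 12.13.1 says it may occur, in a paragraph on mechanism.
- *That the class definitions are seriously defective.* Exactly 10% falls in no class and reverse dippers also meet the non-dipper definition, but both are minor matters of coding.

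**Conclusion.** The point holds as an inefficient choice of analysis for a secondary sub-study endpoint. At the sub-study's own design level (about 54 evaluable per arm, one-sided 2.5%, an effect that ANCOVA would detect with about 80% power), each Fisher test loses more than half of the power in every scenario tried. Non-significant conversion tests would therefore be weak evidence that dipping is unaffected.

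The size rests on assumed dipper prevalence, correlation, normality and a uniform shift, and it shrinks as the effect grows. The main-study co-primary analyses and the sub-study's 24-hour SBP analysis are untouched.

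**What to change.** Make the between-arm dipping comparison an ANCOVA of percent nocturnal SBP fall, 100 x (awake - sleep)/awake, at end of sub-study, with treatment and baseline percent fall as terms. This is the form already used for the other ABPM measures. Keep the conversion percentages as supportive: count reverse dippers as non-dippers, assign exactly 10% to one class, say whether extreme dippers count as dippers, and state whether the denominator is all subjects or those in the starting class.

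The cost is a few lines of analysis-plan wording and one more model on data already collected, with no new visits. The drawback is that the estimate becomes a mean shift in percentage points, less familiar to readers than a dipping category; the retained conversion tables cover that.
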